4.9 OPERATIONAL DEFINITIONS OF VARIABLES

a) Independent variables

i) **Age:** The age of patients (in years) when BPB was performed. Measured and recorded as a strictly positive continuous variable.

ii) **Gender:** The gender of a subject. Recorded as a categorical variable with 0 = male (the baseline group) and 1 = female.

iii) **Ethnicity:** Subject's racial origin. Recorded as a categorical variable with 0 = Malay (the baseline group), 1 = Chinese, 2 = Indian, 3 = Others (such as Siamese)

iv) The American Society of Anaesthesiologist (ASA) grades: Recorded as a categorical variable with 0 =Grade 1 (the baseline group), 1 =Grade 2.

v) **Weight:** The weight of a study participant measured in kilograms measured during he pre-surgical assessment. Recorded as a strictly positive continuous variable.

vi) **Intervention groups:** Recorded as a categorical variable with 0 = 0.75% Ropivacaine only group (the baseline group) and 1 = 0.75% Ropivacaine + adjunct 20 mg parecoxib group.

b) Dependent (outcome) variables

i) **Onset of sensory block:** Time required for a decrease of sensation to 30% or less by comparison to the contralateral limbs as a reference (Duma *et al.*, 2005). Measured in minutes and recorded as a numerical variable.

ii) **Onset of motor block**: the time from injection of local anesthetic mixture until a reduction in motor power to grade 3 or 4 ensued (Ammar and Mahmoud, 2012). Measured in minutes and recorded as a numerical variable.

iii) **Sensory block duration:** The time from injection of local anaesthetic mixture to complete recovery from cold and pain sensation as tested by an alcohol swab and pin prick respective in all dermatomes of the brachial plexus (C5-T1). Measured in hours_and recorded as a continuous variable

iv) **Motor block duration:** the time from injection to complete recovery of motor function in all nerve dermatomes. Measured in hours and recorded as a continuous variable.

v) **Sensory and motor blockades at 30 minutes:** The presence of complete sensory (grade 2) and motor (grade 4) blockades at 30 minutes following the BPB institution.

c) Other relevant clinical variables

i) **Time 1st PCA:** The time taken from the end of the surgery until the delivery of the first PCA morphine. Measured and recorded as a strictly positive numerical variable

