ii) **Volume PCA:** The total volume of PCA morphine administered to the patients after surgery until the patient was discharged from the ward. Measured in mls and recorded as a numerical variable.

iii) PCA demand: The total frequency of morphine demand over a period of 24 hours.Measured and recorded as a strictly positive numerical count variable.

iv) **Sensory block grades:** This was assessed using the a 3-point scale utilised by Crews *et al.* (2002). There are 3 grades for this variable;

- Grade 0 = normal sensory response
- Grade 1 = reduced sensory perception (partial sensory blockade)
- Grade 2 = no sensation (complete sensory blockade).

Recorded as 0 = normal (baseline group), 1 = reduced, 2 = absent.

v) **Motor block grades:** The scale used by Borgeat, Ekatodramis and Durmont (2001) are employed to grade the magnitude of motor block. This scale has 4 grades:

- Grade 1: ability to flex or extend the forearm
- Grade 2: ability to flex or extend only the wrist and fingers
- Grade 3: ability to flex or extend only the fingers
- Grade 4: inability to move the forearm, wrist, and fingers

Recorded as 0 = Grade 1 (baseline group), 1 = Grade 2, 2 = Grade 3, 3 = Grade 4.

vi) **Surgical sites:** The exact location where surgery to the upper limb was carried out. Recorded as 1 = Arm, 2 = Forearm, 3 = Hand, 4 = Fingers.

vii) **VRS :** The visual rating score (VRS) which was recorded at 1, 2, 4, 12, 24 hours post operatively. Its range is between 0 and 10. Recorded as a strictly-positive numerical variable.

viii) **Preoperative VRS:** The VRS recorded prior to supraclavicular BPB.

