 - Motor blockade was also evaluated every 5 minutes up to 30 minutes following the completion of administration of intervention.
 - Motor block was assessed by subject's capability of flexing his / her elbow and hand against gravity. This was then graded according to the scale utilised by Borgeat, Ekatodramis and Durmont (2001).
 - Motor block success was considered achieved when the motor power was reduced to grade 3 or more based on the criteria used by Ammar and Mahmoud (2012).
- Intra-surgical assessment:
 - Requirement of block supplementation, surgical wound infiltration and patient requested sedation or general anaesthesia
 - Surgical anaesthesia success was defined as surgery without the requirements of block supplementation, general anesthesia (administered for incomplete block) or surgical site infiltration

- Haemodynamic monitoring was performed at baseline, after LA injection, after 15 min, 30 min, 1 hour of block procedure & after completing surgery.
- Postoperative assessment:
 - Sensory and motor blockade durations were assessed on half-hourly basis (up to 12 hours postoperatively), during the post surgical period.
 - Patient-controlled analgesia (PCA) morphine or IV tramadol was given as rescue analgesia.
 - Pain scores were assessed using the visual rating scale (VRS) (0-10) where pain was evaluated when the patients were resting at 1, 2, 4, 12, 24 hours postoperatively.
 - The duration of analgesia (time interval from the completion of local anesthetic administration until the first need of rescue analgesia in the form of PCA morphine or IV tramadol) and the amount of morphine or tramadol consumed during the postoperative 24 hours were also documented.
 - Any evidence of complications (e.g., bruises/swelling at the block site, chest pain/ breathing difficulty, dysaesthesia/ muscle weakness in the operated extremity not related to the site of operation) were also recorded.
 - Surgeons were alerted to report any neurological problems not related to surgery during the clinical rounds prior to the patients were discharged from the hospital.
 - Anaesthetic preferences (one of the following: 1) the BPB; 2) block under deep sedation; 3) block under GA).
 - Preferred block for future hand operations was then recorded.

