5.1 THE CLINICO-DEMOGRAPHIC PROFILES OF THE STUDY PARTICIPANTS

[figure not shown]
On the whole, 86 study participants were included in the analysis. The mean age and weight of the participants are similar between the two groups of interventions. Apart from that, both intervention groups exhibit similar patterns of VRS pain score, volumes of local anaesthetics received, supplemental local anaesthetics received and PCA morphine profiles.

With regards to gender and ethnic compositions, both intervention groups, in general, demonstrated similar proportions of females, males and each ethnic groups. Furthermore, both intervention arms have also relatively the same proportions of participants for each ASA grade. Nevertheless, with respect to the specific surgical sites, more study participants in the ropivacaine group had surgeries to their arms whilst more patients in the combined parecoxib-and-ropivacaine group had surgeries to their forearms. Besides, there are also two missing data in this group. However, it can be safely said that proportions of surgical sites are roughly similar in both groups. For further information, refer to table 5.1 and figures 5.1-5.3.

Parameters 1	Parecoxib + Ropi Mean (SD)	vacaine (n=43) n(%)	Ropiva Mean (SD)	caine (n=43) n(%)
Age	43.8 (13.7) 47.5 (26) ^a		46.3 (12.6) 51.0 (21.0) ^a	
Weight (kg)	60.8 (7.6) 60.0 (13.0) ^a		61.6 (7.6) 60.0 (12.0) ^a	
VRS pain score	1.0 (0)		1.0 (0)	
LA volume	20.0 (0)		20.0 (0)	
Supplement LA volume	0.0 (0)		0.0 (0)	
Time to 1 st PCA morphine (hours)	0.0 (0)		0.0 (0)	
PCA Morphine deman within 24 hours (count			0.0 (0)	
PCA Morphine given within 24 hours (count	0.0 (0) s)		0.0 (0)	
Gender Female Male		16 (37.2) 27 (62.8)		0 (46.5) 3 (53.5)
Ethnicity				
Malay Chinese Others		42 (97.7) 1 (2.3) 0 (0)	۷	41 (95.3) 1 (2.35) 1 (2.35)
Surgical sites Forearm Arm Hand Fingers Missing		14 (32.5) 21 (48.9) 0 (0) 6 (14.0) 2 (4.6)		$\begin{array}{cccc} 8 & (18.6) \\ 31 & (72.1) \\ 1 & (2.3) \\ 3 & (7.0) \\ 0 & (0) \end{array}$
ASA grades I II		7 (16.3) 36 (83.7)		6 (14.0) 37 (86.0)
Preoperative VRS scor ^a Median (Interquartile range			0.0 (0.0)	

Table 5.1: The clinico-demographic characteristics of study participants (n = 86)

^aMedian (Interquartile range)

[figure not shown]

Figure 5.1 (a-b): The proportions and percentages of subjects in each intervention arm, as stratified by gender and ethnicity of subjects

[figure not shown]

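### Sections 4.9 c) i-ii and 4.10.2 define time to first rescue and total rescue analgesia differently, and the 4.9 versions omit tramadol and leave some patients without a valid time

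*Combined protocol and SAP*

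**What the plan says.** Section 4.9 c), among the other relevant clinical variables, has three PCA items.

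- **Time to first PCA:** "The time taken from the end of the surgery until the delivery of the first PCA morphine". The entry adds "Measured and recorded as a strictly positive numerical variable".
- **Volume of PCA:** "The total volume of PCA morphine administered to the patients after surgery until the patient was discharged from the ward", in ml.
- **PCA demand:** "The total frequency of morphine demand over a period of 24 hours".

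Section 4.10.2, under postoperative assessment, names PCA morphine or IV tramadol as rescue. It defines duration of analgesia as the "time interval from the completion of local anesthetic administration until the first need of rescue analgesia" in either form, and says that this and "the amount of morphine or tramadol consumed during the postoperative 24 hours" were documented.

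Table 5.1 has a row for time to first PCA morphine in hours and one labelled "PCA Morphine given within 24 hours". Both read 0.0 (0) in both arms.

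**The concern.** Two of the three PCA items in 4.9 conflict with 4.10.2 on time origin, window, unit or drug list. An analyst could follow either section and produce different variables under similar names.

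The 4.9 versions are the weaker pair. Ward discharge comes after randomisation and differs between patients, so the volume is summed over unequal follow-up. It might also depend on how the block wore off. A volume in ml is not a dose until a concentration is given, and 4.9 gives none. Timing from the end of surgery subtracts operation length, which treatment should not affect. A patient who receives tramadol contributes nothing to either variable.

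At stake is whether the trial can say that a longer block led to later or smaller rescue use. Section 5.1 calls the PCA morphine profiles of the two arms similar. A reader cannot tell which definition lies behind that statement.

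**Working it through.** **1. The definitions side by side**

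| | 4.9 c) i-ii | 4.10.2 |
|---|---|---|
| Time: origin | end of surgery | local anaesthetic fully injected |
| Time: event | first PCA morphine delivered | first need of PCA morphine or IV tramadol |
| Time: allowed values | above zero only | not restricted |
| Total: window | surgery to ward discharge | 24 h after surgery |
| Total: drugs | PCA morphine | morphine or tramadol |
| Total: unit | ml | amount, unit not given |

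**2. Patients with no admissible time under 4.9**

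- First rescue at or before the end of surgery: the value is zero or negative.
- Tramadol as first rescue: the event is not counted.
- No rescue: no event, and no censoring rule.

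Table 5.1's time of 0.0 (0) is itself a value that the definition forbids.

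**3. The plan's own figures, as a check on inputs**

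The documents give no figure for rescue analgesia. The nearest is sensory block duration in section 4.11: difference 104 min, SD 140 min, alpha 0.05, power 0.90. Taking alpha as two-sided, n per arm = 2(1.960 + 1.282)² × (140/104)² = 38.1, so 39, as stated. Motor block duration (138, SD 139) gives 21.3, so 22, also as stated. Both match before any allowance for dropout.

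**4. Cost of the end-of-surgery clock (illustration)**

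Assume that time from injection to rescue, T, has the sensory-duration difference and SD, and that operation length S is independent of arm. The 4.9 time is Y = T − S. The expected arm difference in Y equals that in T, because the mean of S cancels. Only the spread grows: SD(Y) = √(140² + SD_S²). Section 4.8.1 gives operations of 1-4 h; if uniform, SD_S = 180/√12 = 52 min. Power uses 43 per arm (section 5.1): Φ(effect × √(43/2) − 1.960).

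| SD of operation length | SD(Y), min | Standardised effect | Multiplier | Power |
|---|---|---|---|---|
| 0 (clock from injection) | 140.0 | 0.743 | 1 | 93.1% |
| 30 min | 143.2 | 0.726 | 0.98 | 92.0% |
| 52 min (uniform 1-4 h) | 149.3 | 0.696 | 0.94 | 89.8% |
| 90 min (half at 1 h, half at 4 h) | 166.4 | 0.625 | 0.84 | 82.6% |

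**5. How often rescue could fall before the end of surgery (illustration)**

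Take T as normal with the reported sensory medians (5.0 and 6.5 h) and SD = IQR/1.349 = 2.0/1.349 = 1.48 h, with S uniform on 1-4 h. By simulation, P(T ≤ S) is about 7.3% in the ropivacaine arm and 0.9% in the parecoxib arm. For a 4 h operation it is about 25% and 4.6%. These figures let full sensory recovery stand in for need of rescue.

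**6. Total until discharge (illustration)**

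If use after 24 h has the same mean in both arms, the absolute difference is the same as at 24 h. With r the ratio of the post-24 h SD to the 24 h SD, uncorrelated, the standardised effect is multiplied by 1/√(1 + r²): 0.97 at r = 0.25 and 0.45 at r = 2. The documents give no value of r.

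**The case against.** The strongest case against is that this is loose wording about side variables. They are absent from the five specific objectives, Table 4.1, the sample size and the abstract's endpoints. Section 4.10.2 already has the better definitions and says the data were documented. PCA demand already uses 24 h, and Table 5.1 labels the amount given as within 24 h, so the discharge window was apparently not the one reported. Rescue is listed under postoperative assessment, and failure during surgery is recorded separately as supplementation, infiltration or general anaesthesia. Rescue before surgery ends may therefore be rare. All of this stands, and it keeps the point minor.

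A reader might go further and infer that 4.9 shrinks the arm difference by discarding patients with early rescue, mostly controls. Under the assumptions of step 5, deleting non-positive times would cut a 90 min difference to about 77 min. With the planning values (means 439 and 543 min, SD 140), 104 min would fall to about 97. But the documents contain no deletion rule. Section 4.13 specifies intention to treat and multiple imputation. Section 4.9 also applies the strictly positive label to a pain score ranging from 0 to 10 and to PCA demand, which Table 5.1 shows as 0.0 (0), so it is not enforced as an exclusion. Keeping such patients as zero gives about 87 and 103 min.

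A reader might also infer that totals to discharge push towards no difference. The direction is not established: if shorter blocks led to later discharge, these totals would widen the gap.

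**Conclusion.** The inconsistency is real and needs no assumption: different origins, windows, units and drug lists for what should be the same two variables, and three kinds of patient with no admissible time under 4.9.

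Its numerical effect is small and only illustrative. The end-of-surgery clock multiplies the standardised effect by about 0.94 (range 0.84 to 0.98) and takes power from about 93% to 90% (range 83% to 92%). This holds only if rescue time behaves like sensory block duration and operation length is unrelated to arm. Bias in the expected difference is not shown.

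With time to first PCA and morphine given both reported as 0.0 (0) in each arm, there is no reported rescue difference to distort. No primary endpoint, sample size or block-duration conclusion changes. Minor, but worth correcting, because the rescue results cannot be interpreted until one definition is fixed.

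**What to change.** Replace 4.9 c) i-ii with the 4.10.2 definitions.

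- **Time to first rescue:** from completion of the local anaesthetic to the first PCA morphine or IV tramadol, with patients without rescue censored at 24 h. State once whether the event is need or delivery, since the two sections differ.
- **Total rescue:** mg over a fixed 24 h after surgery, shown separately for morphine and tramadol, with the PCA concentration stated so that ml convert to mg. A combined morphine-tramadol total is optional; if used, fix the conversion before analysis.
- **Wording and reporting:** delete the strictly positive requirement and report both variables by arm. Show patients without rescue as censored, not as zero hours.

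The cost is a wording change and re-derivation from data that 4.10.2 says were recorded. The one loss is that use after 24 h no longer counts.

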 - After skin preparation and draping, the probe was next placed in the supraclavicular fossa and subcutaneous infiltration will be given on the targeted needle side

- The needle was then inserted from lateral to medial direction in the long axis of the transducer (in-plane technique).
- Nineteen (19) ml of 0.75% ropivacaine and 1 ml of 20 mg of parecoxib
 (Group I: parecoxib + ropivacaine) or 19 mls of 0.75% alone plus 1 ml of
 normal saline (Group II: ropivacaine alone) was then injected at the
 "corner pocket". Adrenaline was not added into any solution.
- The remaining 5 ml was later injected to a point approximately level with the superior/ cephalad aspect of the subclavian artery, but no further than 1 cm lateral to the artery

Block performance-related pain was then evaluated immediately after removing the needle by asking the patient to verbally quantify the level of pain using a score between 0 to 10 (0 meaning no pain, 10 meaning excruciating pain). The study participants were withdrawn from the trial and rescue medications were given if one of the following withdrawal criteria occurred:

- Patient developed local anaesthetic toxicity (seizure)
- Patient developed hemodynamically instability bradycardia/hypotension)
- Patient developed anaphylaxis

The procedures for the assessment of sensory and motor block are as follows:

- Assessment of sensory block:
 - Sensory blockade was assessed every 5 minutes up to 30 minutes following the completion of administration of intervention.
 - Sensory loss was confirmed by the loss to cold sensation using 10 mls cold saline bottle and pinprick sensation using 23G needle in all dermatomes supplied by the brachial plexus (C5-T1).
 - Time zero was defined as the time at which LA was completely injected.

- Sensory block success was defined as complete pin-prick sensory blockade (grade II based on the grading scale employed by Crews *et al.* (2002)) in all dermatomes of the brachial plexus (C5-T1).
- The block was considered incomplete if any supplemental local anesthetic is needed for complete anesthesia.
- The block was considered failed if the desired volume did not provide complete anesthesia or conversion to general anaesthesia was required prior to surgery.
- General anaesthesia was routinely performed with intravenous induction (sedation) agent, short acting opiods and muscle relaxant
- Assessment of motor block:

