6.1 THE ANTI-NOCICEPTIVE EFFECTS OF PARECOXIB IN SUPRACLAVICULAR BRACHIAL PLEXUS BLOCK

In this study, our primary finding is that synergistic combination of ropivacaine and parecoxib only prolonged the duration of sensory and motor blockades, not the onset of sensory and motor block. This proves that COX-2 inhibitors act centrally and that the spinal transmission of nociceptive signals is affected by constitutively-expressed COX-2 in the central nervous system. More generally, our results indicate that the antiinflammatory and antinociceptive effects of COX-2 inhibitors are not necessarily related since the dosage we used in this study was well below the dose required for antiinflammatory induction. However, the discrepancy between our findings and Liu et al. (2013) in terms of the onset of sensory and motor blockades can be attributed to the higher concentration of ropivacaine (0.75%) compared to one used by Liu et al. (2013) (0.25%) ropivacaine). As a result, Liu et a. (2013) reported a significant difference with regard to the onset of sensory and motor blockades between 0.25% ropivacaine + parecoxib recipients and those who received 0.25 % ropivacaine only. Therefore, our finding adds to the current knowledge by demonstrating the attenuation of 20 mg parecoxib's effect when it is used as an adjunct to a higher concentration of ropivacaine. Besides, we also generalised the findings and conclusion made by Liu et al. (2013), who only recruited subjects who were recipients of axillary brachial plexus blockade, by demonstrating that the benefits of adjunct parecoxib can also be extended to patients undergoing BPB via supraclavicular approach as well. We also sucessfully managed to control the confounding effects of preoperative (baseline) pain scores since both intervention groups exhibited identical mean visual rating scores (VRS). Consequently, the validity of our findings is more bona fide than the ones asserted by Liu *et al.* (2013).

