- Zeilhofer HU. The glycinergic control of spinal pain processing. Cellular and Molecular Life Sciences 2005;62(18):2027-35.

CASE REPORT FORM (CRF)

CASE NO

GROUP: SCB / ICB

DATA COLLECTION SHEET: EFFECT OF PARECOXIB 20MG AS AN ADJUNCT IN 0.75% ROPIVACAINE TO ULTRASOUND GUIDED SUPRACLAVICULAR BLOCK FOR UPPER LIMB SURGERY

PRE OP SCREENING:			
INCLUSION CRITERIA	TICK (√)	EXCLUSION CRITERIA	(X)
Adult (age 18 to 60)		Patient refusal for BPB	
ASA I to II		Known case of allergic to parecoxib and local anesthesia	
Expected duration of surgery 1-4 hours		History of previous brachial plexus injury	
		Pregnancy	
		History of chronic pain, those that using chronic analgesic medication	
		Coagulapathy	
		Systemic infection or local infection at site of injection	
		History of Ischaemic Heart Disease.	
		History of Renal failure	
		History of Atopy	

BACKGROUND DATA

Date:

Full Surgical Procedure:

SITE OF SURGERY	CODING	TICK ($$)	
Arm	1		
Forearm	2		
Hand	3		
Fingers	4		
R/N: Sex: M/H			
Age: Sex: M/F	F E	Ethnicity: M / C	/I /Others
ASA: I / II			
If ASA II, state the disease/s Height: cm Weight: _			
	k	g	
BLOCK TECHNIQUE	100		
• Size of the needle: 50 / 80/			
• Depth of skin to superior pa			
• VRS of procedure-related p	aın (1 to 10)	:	
• Volume of LA given:	ml		
• Supplement volume of LA	given:	ml	
• Time of completing LA inje	ection:		
• Time of sensory block onset (reduce sensation ≤ 25% from contralateral side):			
Onset of sensory block:	mi	n	
• Time of motor block onset	(reduce mot	or power $\leq 25\%$	from contralateral side):
Onset of motor block:	min		

• Assessment of sensory block after 30 min:

SENSORY BLOCK	TICK ($$)
2 (Normal)	
1 (partial block/ reduced)	
0 (Complete block/ absent)	

• Assessment of motor block after 30 min:

GRADE	TICK ($$)
1 (able to flex or extend the forearm)	
2 (able to flex or extend only the wrist	
and fingers)	
3 (able to flex or extend only the	
fingers)	
4 (unable to move the forearm, wrist,	
and fingers)	

QUALITY OF OPERATIVE CONDITIONS

QUALITY OF OP	Please tick ($$)
4 (Excellent/ No complaint from patient)	
3 (Good/ Minor complaint with no need for the	
supplemental analgesics)	
2 (Moderate/ Complaint that required supplemental	
analgesia)	
1(Unsuccessful/ Patient given general anaesthesia)	

SITE REQUIRED SUPPLEMENT BLOCK

PATCHY BLOCK SITE	Please tick ($$)

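### Procedure pain is scored 0–10 in the methods but 1–10 on the CRF, so the unlabelled VRS of 1.0 (0) in both arms of Table 5.1 cannot be interpreted or cited as comparability

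*Combined protocol and SAP*

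**What the plan says.** The document uses three separate pain scores.

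- **Procedure-related pain.** Section 4.10.2 asks for it immediately after the needle is removed, on a 0 to 10 scale: "0 meaning no pain, 10 meaning excruciating pain". On the CRF, under Block technique, the field that begins "VRS of procedure-related" is marked 1 to 10 and has no anchors.
- **Postoperative VRS.** Section 4.9, item c) vii, reads "The visual rating score (VRS) which was recorded at 1, 2, 4, 12, 24 hours post operatively" and continues "Its range is between 0 and 10. Recorded as a strictly-positive numerical variable". The postoperative assessment in section 4.10.2 again gives 0–10.
- **Preoperative VRS.** Section 4.9, item c) viii, says only "The VRS recorded prior to supraclavicular BPB" and gives no range of its own.

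Under the Mean (SD) heading, Table 5.1 has a row for VRS pain score, 1.0 (0) in both arms (n = 43 each), with no measure or time point named. A separate preoperative row shows 0.0 (0.0) in its legible cell. Section 5.1 comments that "both intervention groups exhibit similar patterns of VRS pain score, volumes of local anaesthetics received". Section 6.1 says that confounding by preoperative pain was controlled "since both intervention groups exhibited identical mean visual rating scores (VRS", and infers that the findings are more valid than those of the earlier axillary-block trial of parecoxib with ropivacaine.

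**The concern.** A form that starts at 1 has no place for the protocol's value for no pain. If the form was followed as printed, a recorded 1 could mean no pain or slight pain. The only VRS pain score reported apart from the preoperative one is exactly 1 in both arms, and the text uses that equality to describe the arms as alike.

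Two things are at stake. One is whether the comparability statement has any content. The other is whether a reader can tell if the longer sensory block (median difference 1.5 hours) came with less pain. The scores that would answer the second question were planned but are not shown.

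**Working it through.** There are no patient-level scores, so 1.0 (0) cannot be rebuilt. What can be checked is what the figure is compatible with.

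**1. Scales side by side.**

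| Measure | One place | Another place |
|---|---|---|
| Procedure pain | 0–10, 0 = no pain (4.10.2) | 1–10 (CRF) |
| Postoperative VRS | 0–10 (4.9 and 4.10.2) | greater than 0 (4.9) |
| Preoperative VRS | no range stated (4.9) | – |

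The first two rows are contradictions about the same measurement.

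**2. Which score is the 1.0 row?** Table 5.1 lists VRS pain score, LA volume, then supplementary LA volume. The CRF lists procedure VRS, LA volume, then supplementary LA volume. The matching order makes procedure pain the probable identity. This is an inference, not a statement in the document.

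**3. What 1.0 (0) implies on its face.** Take whole-number scores with n = 43, and let k patients lie one point from 1, all in the same direction. Then mean = 1 ± k/n and SD = √[k(n − k)/(n(n − 1))].

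| k | Mean | SD |
|---|---|---|
| 0 | 1.000 | 0.000 |
| 1 | 0.977 or 1.023 | 0.152 |
| 2 | 0.953 or 1.047 | 0.213 |
| 3 | 0.930 or 1.070 | 0.258 |

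If the SD is exactly 0, all 43 patients in each arm have a recorded score of 1. If the SD was rounded to a whole number, at most 2 per arm could differ in this way before the mean stopped printing as 1.0.

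**4. What it could hide.** Assume that a true 0 was entered as 1. With k pain-free patients and the rest truly at 1, the true mean is (43 − k)/43.

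| Pain-free, of 43 | True mean | Recorded |
|---|---|---|
| 0 | 1.00 | 1.0 (0) |
| 10 | 33/43 = 0.77 | 1.0 (0) |
| 21 | 22/43 = 0.51 | 1.0 (0) |
| 43 | 0.00 | 1.0 (0) |

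Under this assumption the arms could lie at opposite ends, a true difference of 1.00 − 0.00 = 1.00 point, and still print identically.

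**5. Timing.** Section 4.10.2 takes the procedure score after needle removal, hence after the allocated solution has been injected. If the row is procedure pain, it is not a baseline characteristic.

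**6. Planned but not shown.** Five postoperative readings in 86 patients make up to 5 × 86 = 430 values. Section 5.3 and Tables 5.1 to 5.5 give none by time point, and no caption of Figures 5.1 to 5.9 describes them.

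**7. Section 6.1.** This sentence is about the preoperative score, reported in its own row. Equal values at the bottom of a scale say little about comparability in pain sensitivity, and section 6.4 itself concedes that this score is not an accurate measure of pain tolerance.

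**The case against.** The strongest reply is that this is loose drafting around a secondary variable. VRS is listed among the other clinical variables, outside the objectives, the hypotheses and Table 4.1, and no onset, duration or 30-minute comparison uses it. The strictly-positive label appears to be a slip for non-negative: time to first PCA carries the same label and is reported as 0.0 (0) in both arms. Table 5.1 is titled as clinico-demographic and openly includes postoperative PCA use. The confounder-balance statement in section 5.3.4 rests on tables that contain no VRS. Recruitment ended on 28 August 2017, so changing the form alters no data.

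Most of this stands, and it limits the point to interpretation and reporting. It does not explain what 1.0 (0) means, or why section 5.1 cites that row.

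A reader might also infer more than the documents support:

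- *That section 6.1 rests on the ambiguous 1.0.* It does not; it concerns the preoperative score. The weakness there is the inference drawn from equal floor values.
- *That pain-free patients were recorded as 1.* No text says how a zero was entered.
- *That the pain-free share is either 100% or 0%.* Step 4 shows that any share in between fits.
- *That a preoperative 0.0 breaks the strictly-positive rule.* That wording belongs to the postoperative item.
- *That the whole CRF uses 1 to 10.* This is shown for the procedure field only.
- *That pain is the only patient-reported outcome.* Section 4.10.2 also records anaesthetic preferences.

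**Conclusion.** The scale contradictions are real: procedure pain is defined on 0–10 and collected on 1–10, and the postoperative VRS is both 0–10 and strictly positive. As reported, 1.0 (0) cannot separate no pain from slight pain in everyone, so it cannot carry the section 5.1 statement of similarity. If a zero was entered as 1, the pain-free share in either arm is unconstrained between 0% and 100%. The postoperative VRS is missing by arm and time point from the results text and tables. The claim in section 6.1 of greater validity than the earlier trial does not follow from equal preoperative scores.

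This rests on two assumptions: that the 1.0 row is procedure pain (from its position in the table), and, for the 0–100% range only, that zeros became ones. It is an inconsistency that should be corrected. It affects the comparability statements and the pain reporting, and leaves the block results as they are.

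**What to change.** 1. Give each VRS one anchored range, 0 = no pain to 10, in section 4.9, section 4.10.2 and the CRF, and replace the strictly-positive wording with non-negative. With recruitment closed, this corrects the record and any reuse of the form.
2. Label the Table 5.1 row with its measure and time point, and move it to the outcomes if it was taken after the block.
3. State what a recorded 1 meant. If that cannot be established, mark the score as uninterpretable.
4. Report the collected postoperative VRS by arm at 1, 2, 4, 12 and 24 hours.
5. Limit the comparability statement to the preoperative score, and drop the section 6.1 inference of greater validity.

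The cost is one extra descriptive table from data the protocol already collects, some relabelling, and a less favourable comparability statement. No new data are needed.
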